To measure the energy expenditure using indirect calorimetry in mechanically ventilated children admitted to the intensive care unit before, during and after fever.

HYPOTHESIS

Null hypothesis: Fever will be associated with <10% difference of baseline energy expenditure per 1°C change in temperature in critically-ill children ventilated on the intensive care unit

Alternative hypothesis: Fever will be associated with a >10% difference of baseline energy expenditure per 1°C change in temperature

STUDY DESIGN

Prospective observational cohort study

STUDY POPULATION

Children admitted to the paediatric intensive care unit at Great Ormond Street Hospital with suspected infection, following trauma or major surgery, who are likely to develop a fever.

ELIGIBILITY CRITERIA

Inclusion criteria:

- Children >10kg (The MedGraphic Ultima CCM calorimeter has been used safely in children as low as 10kg)
- Children with suspected infection, following trauma, or post-major surgery

Exclusion criteria:

- Children post brain injury
- Children with refractory status epilepticus
- Children post cardiac arrest
- Children post cardiac bypass
- Children with cardiac arrhythmias
- Children not invasively ventilated
- Children with a greater than 5% leak around their endotracheal tube
- Children with a fraction of inspired oxygen (FiO_2)>0.60
- Children above 16 years of age

STUDY OUTCOMES

Primary outcome: Change in energy expenditure per degree Centigrade change in temperature

Secondary outcome: Change in oxygen extraction ratio (ratio of oxygen consumption to oxygen delivery) per degree Centigrade change in temperature using oxygen delivery data from the Lidco Rapid (LIDCO Ltd, UK) cardiac output monitor if in place.

STUDY PROCEDURES

Screening and Recruitment

- All patients will be screened each morning (Mon-Fri) by the PI for weight, ventilation status and likelihood of developing a fever (The PI is part of the wider clinical team)
- The PI will ask the clinical team on call if calorimetry is suitable for the identified patient/s
- If the clinical team feel this is appropriate, the PI will ask consent of the parents to undertake indirect calorimetry

Study procedure

1. Once consented, calorimetric measurement will be undertaken using the MedGraphic Ultima CCX, Minnesota, USA). This will be done in the following steps:
 - a. Assess the patient for stability:

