During measurement we will monitor the child's respiratory rate, oxygen saturation levels and end tidal CO₂. If any of these values change significantly, as judged by the bedside nurse or the PI, calorimetry will be discontinued.

Data collection

Data will be collected for

- Demographic data (ID, weight, height, age, sex, diagnosis)
- Inspired and expired O₂ and CO₂; VO₂ and VCO₂; Respiratory Quotient; Energy expenditure (as measured and displayed by the MedGraphics Ultima CCM calorimeter)
- Physiological variables (heart rate, blood pressure)
- IF CARDIAC OUTPUT MONITOR IN PLACE: stroke volume and cardiac index (as measured by Lidco Rapid, LIDCO Ltd, UK) and latest haemoglobin
- Inotrope infusion doses
- COMFORT or sedation score as recorded
- Paralysis (yes/no)
- Temperature
- Nutritional intake in last 24 hours or since admission

Data apart from demographic data will be collected at the start of each recording and hourly if continuous recording

If cardiac monitoring is in place, continuous data (as recorded by the Lidco Rapid) will be used to calculate oxygen delivery.

STATISTICAL ANALYSIS

Sample size: Not enough data exists to ascertain the standard deviation of energy expenditure using the Medgraphics Ultima CCM calorimeter in critically ill children over the time period to be measured. However a standard deviation of 10% has been observed in critically ill children by groups who have measured energy expenditure in large numbers of children (personal communication from Dr [name], Imperial College, London). Based on this, for a 10% effect size, with a one-tailed α of 0.05 and (1- β) of 0.8, a sample size of 10 children would be needed, provided a 1°C of temperature is seen. An analysis of temperature change following over 5000 doses of paracetamol in febrile children suggested a mean reduction of temperature by 0.7°C. Based on this therefore we will need $10 \times 1/0.7 = 15$ patients

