However it is likely that our sample will have several confounders which will need to be taken into account by multi-variable analysis. Therefore we will aim to recruit at least 15 children with measurements with and without fever (ideally before-during and after fever), but will try and recruit as many children as possible over the 12 month study period. Approximately 300 patients admitted to PICU at Great Ormond Street Hospital per year are above 10kg. Of these, approximately 75-100 patients are electively admitted, 30 post-major surgery (mostly spinal surgery). 30% of children post spinal surgery develop a fever in the first 24 hours. In addition the remaining 200 children are admitted as an emergency. 80% of children admitted as an emergency are treated for a suspected infection, the remainder post trauma. Again 30-50% of children admitted with an infection or trauma develop a fever within the first 24 hours. Therefore each year approximately 75-80 patients will be >10kg, ventilated, and will develop a fever within the first 24 hours of admission, with a proportion developing fever later on in admission (e.g. from nosocomial infections).

Statistical analysis: Uni-variable analysis using paired t-tests will be undertaken by comparing the energy expenditure with and without fever, divided by the change in temperature. Multi-variable analysis using a multi-level regression model will be used using

- Change in energy expenditure as the outcome variable
- Patient ID as the random effect variable
- Change in temperature, COMFORT score, vasoactive inotrope score, heart rate, blood pressure, and paralysis as a binary variable as fixed effect variables

If cardiac output monitoring is in place, then the oxygen extraction can be calculated as VO_2/DO_2 , where,

$DO_2 = \{cardiac\ index \times ((oxygen\ saturation\ of\ haemoglobin \times haemoglobin\ concentration) + 0.0031 \times partial\ pressure\ of\ oxygen)\}$

and VO_2 is measured from the calorimeter

ETHICAL CONSIDERATIONS

The study will be conducted in accordance to Good Clinical Practice principles and the principles of the Declaration of Helsinki.

Informed consent will be sought from parents/guardians with parental responsibility prior to measurement. Consent forms will be stored in the Great Ormond Street Critical Care Research Office securely.

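### The oxygen-delivery formula lacks the oxygen-binding constant and all units, and nothing puts calorimeter VO2 on the same per-m² basis as cardiac index

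*Combined protocol and SAP*

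**What the plan says.** STUDY OUTCOMES names one secondary outcome: "Change in oxygen extraction ratio (ratio of oxygen consumption to oxygen delivery) per degree Centigrade change in temperature", available only in children who have a cardiac output monitor.

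The STATISTICAL ANALYSIS section gives the calculation: "If cardiac output monitoring is in place, then the oxygen extraction can be calculated as VO_2/DO_2". DO2 is cardiac index multiplied by a bracket with two terms: saturation times haemoglobin, plus 0.0031 times PO2. No multiplier stands on the haemoglobin term, and no unit is given for any quantity. The section closes with "and VO_2 is measured from the calorimeter".

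The Data collection section lists, for monitored children, "stroke volume and cardiac index (as measured by Lidco Rapid, LIDCO Ltd, UK) and latest haemoglobin". VO2 belongs to a list item that ends "Energy expenditure (as measured and displayed by the MedGraphics Ultima CCM calorimeter", again without a unit. Weight, height and heart rate are collected, but no section calculates BSA or turns cardiac index back into cardiac output.

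Under Patient safety, the team watches "respiratory rate, oxygen saturation levels and end tidal" CO2 during measurement. Neither saturation nor PO2 appears in the data list or in step 1b of the study procedure.

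**The concern.** There are three parts, which differ in certainty.

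- **Missing constant and units (certain).** Saturation × haemoglobin is grams of haemoglobin per volume of blood. The dissolved term is a volume of oxygen per volume of blood. Without a factor for mL of oxygen per gram, the sum has no meaning and DO2 comes out too low. The formula is printed as a complete expression with no gap or redaction mark, so loss in text extraction is unlikely.
- **Unmatched bases (conditional).** An index is per m². If VO2 is a whole-body rate, the plainer reading because no indexing is mentioned, VO2/DO2 carries BSA as a multiplier that differs from child to child.
- **Inputs not listed (minor).** Saturation multiplies the dominant term but is only monitored for safety. PO2 is not listed either.

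At stake are the reported extraction levels and, on an absolute scale, the size of the change per °C. The missing constant inflates every child by nearly the same factor. The BSA error does not: in any pooled absolute change, larger children would weigh more. Eligibility runs from above 10 kg to 16 years, so a wide range of body size is built in.

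**Working it through.** The plan states no DO2 or extraction value, so there is no figure of its own to reproduce. The check evaluates the printed formula with and without the constant.

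**Inputs.** From the plan: the form of the formula and the coefficient 0.0031. Assumed, because the documents give no values: binding constant k = 1.34 to 1.39 mL/g; Hb 10 g/dL (range 7 to 14); saturation 0.97 (0.90 to 1.00); PO2 90 mmHg (60 to 150); cardiac index 4 L/min/m², held fixed; VO2 rising from 150 to 165 mL/min/m²; one child of 10.5 kg and 78 cm, another of 55 kg and 165 cm.

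**1. Oxygen content per dL**

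- As printed: 0.97 × 10 + 0.0031 × 90 = 9.979
- k = 1.34: 1.34 × 9.7 + 0.279 = 13.277; ratio 13.277/9.979 = 1.330
- k = 1.39: 1.39 × 9.7 + 0.279 = 13.762; ratio 13.762/9.979 = 1.379
- Over the full assumed ranges: 1.317 to 1.336 (k = 1.34) and 1.363 to 1.385 (k = 1.39)
- Dissolved share: 0.279/13.277 = 2.1%, so PO2 matters little

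**2. Extraction ratio, VO2 and DO2 both indexed.** A factor of 10 (dL to L) is needed with these units. The printed formula does not contain it; it is supplied here to isolate the effect of the constant.

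- DO2 with k = 1.34: 4 × 10 × 13.277 = 531.1 mL/min/m²
- DO2 without k: 4 × 10 × 9.979 = 399.2
- With k: 150/531.1 = 0.282 to 165/531.1 = 0.311, change 0.028
- Without k: 150/399.2 = 0.376 to 165/399.2 = 0.413, change 0.038

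**3. If VO2 is also whole-body**

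- BSA = √(height × weight/3600): √(78 × 10.5/3600) = 0.477 m²; √(165 × 55/3600) = 1.588 m²; ratio 3.33
- The same true change of 0.028 then reads 0.477 × 0.0376 = 0.018 in the small child and 1.588 × 0.0376 = 0.060 in the large one

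**4. Percentage scale.** 165/150 − 1 = 10.0% in every case above. BSA cancels exactly. The constant cancels exactly if blood oxygen content is unchanged and nearly so otherwise: if PO2 moves from 90 to 150 mmHg, the ratio is multiplied by 0.982 as printed and by 0.986 to 0.987 with the constant.

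**5. Sensitivity to unstated units**

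- Without the factor of 10: 4 × 9.979 = 39.9, and 150/39.9 = 3.76, an impossible extraction ratio
- Hb in g/L: 4 × (97 + 0.279) = 389.1, and the overstatement is 531.1/389.1 = 1.36 (k = 1.34) to 550.5/389.1 = 1.41 (k = 1.39)
- Saturation entered as 97 instead of 0.97: DO2 = 4 × 10 × (970 + 0.279) = 38,811 instead of 399
- PO2 of 12 kPa entered in place of 90 mmHg: corrected DO2 is 521.4 instead of 531.1, about 2% lower

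**The case against.** The best defence is the percentage scale. The primary outcome is worded in parallel, and the hypothesis expresses it as a percentage of baseline. If the secondary outcome is read the same way, BSA drops out and the constant almost does. This stands as far as it goes, but the 10%-of-baseline wording concerns energy expenditure only, and the plan states no scale for extraction. Extraction levels would be wrong on either scale.

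Even on the absolute scale, both errors act as positive multipliers. The direction of change in each child survives, apart from a trivial dissolved-oxygen effect. The example holds cardiac index fixed, which makes the change more visible. The adult cooling study described in BACKGROUND saw cardiac output fall and extraction stay constant; if children respond likewise, a scale error has little change to distort. These points limit the harm but do not make the formula usable.

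The BSA part depends on a device unit that the documents do not give, and disappears if VO2 is already indexed. The weighting of larger children is also hypothetical, since the t-tests and the regression are specified for energy expenditure only. Both are fair, and this part remains conditional.

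The Data collection section says that continuous monitor data will be used for oxygen delivery. Which fields that record holds is not stated. Saturation and PO2 might also be retrievable from clinical records, so their absence from the list is a small point.

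Finally, an analyst would probably use the standard formula anyway. That concedes that the printed one should not be followed.

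**Conclusion.** The concern holds. As printed, the DO2 formula is dimensionally wrong and cannot be applied without supplying a constant and units that the plan omits. With Hb in g/dL and volume units aligned, extraction and its absolute change are overstated 1.32- to 1.38-fold over the assumed ranges; with Hb in g/L at the central values, 1.36- to 1.41-fold. If VO2 is a whole-body rate, BSA adds a further 3.3-fold spread between the two assumed children; if it is already indexed, that part vanishes. All physiological inputs are assumptions.

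The consequence is confined to the only secondary outcome, in children with a cardiac output monitor. The primary outcome and the sample size are untouched. It should be fixed, but it does not threaten the study's main question.

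**What to change.** - Replace the formula with DO2 = cardiac index × 10 × [(1.34 × saturation × Hb) + 0.0031 × PO2], with cardiac index in L/min/m², saturation as a fraction, Hb in g/dL and PO2 in mmHg (convert if reported in kPa). This gives DO2 in mL/min/m².
- State the unit in which the calorimeter reports VO2, and use one basis throughout: either VO2 divided by BSA (from the collected weight and height) with cardiac index, or whole-body VO2 with cardiac output (stroke volume × heart rate, both collected).
- State whether the change in extraction per °C is absolute or a percentage of the child's baseline.
- Add saturation and the latest routine PO2 to the data list for children with a cardiac output monitor.

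The cost is a corrected formula, a sentence on units and scale, and two fields from routine monitoring and blood gases. The formula and indexing can be corrected at analysis. Only saturation and PO2 need attention during the study, so that values matching each measurement are available. No new procedure is needed.

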Measuring the metabolic cost of fever: Indirect calorimetry in children with fever on the intensive care unit.

Protocol Version 2 (07.08.2016)

STUDY INVESTIGATORS:

Principal Investigator: [name]
PhD Student,
Respiratory, Critical Care and Anaesthesia Section,
UCL Great Ormond Street Institute of Child Health, London, UK
[contact]

Chief Investigator: [name] [name]
[name] Care Medicine
Respiratory, Critical Care and Anaesthesia Section,
UCL Great Ormond Street Institute of Child Health, London UK
[contact]

INTRODUCTION

Fever is a common immune response in children with infection or inflammation. While fever may potentiate the immune system to fight the pathogenic stimulus, energy is required to generate the raised temperature. This may be scarce in critical illness, particularly in children. We do not know how much energy is used in generating fever by children in the intensive care unit. This study aims to measure energy expenditure in children during and before/after they have a fever. We aim to do this using indirect calorimetry in at least 15 children, who are invasively ventilated on the intensive care unit. We will then calculate the average increase in energy expenditure required per 1°C rise in temperature in this population. If fever does not require a significant increase in energy expenditure in children on the intensive care unit, then treatment of fever may not have any benefits. If fever does require an increase in energy expenditure, this may counter the immunological benefits that fever confers. In such a case a randomised controlled trial comparing treatment and non-treatment of fever would be required.

BACKGROUND

Fever is an innate immune response to danger. Stimuli such as pathogens or tissue damage lead to a cascade of cytokine signals, including the release of pro-inflammatory cytokines such as TNF- α , IL-6 and IL-1. Many of these pro-inflammatory cytokines act upon the thermoregulatory centre of the hypothalamus via the release of prostaglandins, to increase the body's temperature set-point. The body responds by both reducing heat loss and increasing heat production to raise the body temperature^{1,2}.

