The energy requirements of fever have previously been measured in adult patients on the intensive care unit. Manthous et al studied 12 febrile patients on the intensive care unit during cooling after sedation and paralysis. For each 1°C drop in temperature, the reduction of energy expenditure was 10% of the baseline. This was also accompanied with a reduction in cardiac output, and no change in oxygen extraction (the ratio between oxygen consumption and delivery)²⁶. Similar associations between temperature reduction and decrease in energy expenditure with cooling have been demonstrated in the context of brain injury²⁷⁻²⁸.

In children, energy expenditure has been shown not to be raised in febrile infants admitted to hospital. In a cohort of 12 children, although 8 had an increase in energy expenditure when febrile, overall there was no difference²⁹. However this was conducted in children who were not critically unwell or in intensive care. It is possible that these children were able to increase their temperature by preventing heat loss. Children in intensive care may not have the ability to do so, due to disease related factors such as shock and vasoplegia, or treatment related factors, such as exogenous vasodilators. Children admitted to hospital with over 40% burns had an increase in energy expenditure with fever by up to 30% of baseline³⁰. These children were likely to have more unregulated surface heat loss due to skin barrier compromise, but equally were likely to be hypermetabolic following their initial injury. In an analysis of cytokine levels and metabolic rate in critically-ill children, Briassoulis et al found that the predominant metabolic pattern in acute critical illness in children was that of hypometabolism, during which energy expenditure did not correlate with levels of IL-6 and IL-10, both fever-inducing cytokines³¹.

Therefore we still do not know if energy expenditure is increased in children with febrile illness in the intensive care unit. Given the immune benefits of fever, there may be an argument to not treat fever in critically ill children as any advantage in host response may be beneficial. However, if the energy expenditure associated with fever is high, treatment of fever may have a benefit.

AIM OF STUDY

To understand the changes, if any, in the energy expenditure of critically-ill children with fever

STUDY OBJECTIVES

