Data will be stored and processed electronically in a secure password protected NHS IT network according the principles of the institutional information governance policy. Patient identifiable data will be minimised to unique patient hospital number. The storage of data will be consented for.

Baseline energy expenditure data may be shared with collaborators anonymously to further the understanding of metabolic activity in critically ill children. Consent for this will explicitly sought.

OUTCOMES AND SIGNIFICANCE

If the null hypothesis is true, then the treatment of fever in critically-ill children can be questioned, especially given the immunological benefits. If the alternative hypothesis is true, then the overall risk- benefit balance of treating or not treating fever in critically ill children will have to be assessed in the form of a randomised controlled clinical trial.

Research findings will be disseminated in national and international intensive care conferences, and peer-reviewed medical/scientific journals

REFERENCES

4. Kluger MJ. Fever in the frog *Hyla cinerea*. *J Therm Biol.* 1977;2:79-81
7. Stitt JT. Prostaglandin E1 fever induced in rabbits. *J Physiol.* 1973 Jul;232(1):163-79

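### The plan acts on the 10% per °C null being true, but no planned analysis could show that, and the Introduction words the trigger differently

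*Combined protocol and SAP*

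**What the plan says.** All references are to the combined protocol and SAP.

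- **Hypothesis.** The threshold is 10% per degree: "Null hypothesis: Fever will be associated with <10% difference of baseline energy expenditure per 1°C change in temperature" and "Alternative hypothesis: Fever will be associated with a >10% difference of baseline energy expenditure per 1°C change in temperature".
- **Outcomes and Significance.** One consequence is attached to each hypothesis: "If the null hypothesis is true, then the treatment of fever in critically-ill children can be questioned, especially given the immunological benefits"; and "If the alternative hypothesis is true, then the overall risk- benefit balance of treating or not treating fever" is to be assessed in a randomised trial.
- **Introduction.** Similar consequences are attached to other triggers. "If fever does not require a significant increase in energy expenditure in children on the intensive care unit", treatment may bring no benefit. "If fever does require an increase in energy expenditure, this may counter the immunological benefits that fever confers", and a randomised trial is then needed. Neither sentence mentions 10%.
- **Background.** A third wording is used: "if the energy expenditure associated with fever is high, treatment of fever may have a benefit". The word for a large cost is not defined.
- **Statistical Analysis.** The analyses are paired t-tests of energy expenditure with and without fever, divided by the temperature change, and a multi-level regression. The sample size uses a 10% effect, an SD of 10%, one-tailed 5% and 80% power, giving 10 children, raised to 15 for an expected temperature change of 0.7°C. Fifteen is a minimum.

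No section gives a confidence interval, a test against 10%, a criterion for accepting the null, or an outcome in which the data do not settle the matter.

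**The concern.** A t-test can reject a null but cannot establish it. The Outcomes and Significance section nevertheless draws its practical message from the null being true and does not say how that would be decided. The easiest reading open to an author or reader is that a non-significant result means a low cost. On that reading, imprecise data make the message that treatment can be questioned more likely, not less.

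The second difficulty is the trigger. A cost clearly above zero but not shown to exceed 10% per °C satisfies the Introduction's wording for a trial. It also leaves the 10% null unrejected, which could be taken as the branch that questions treatment. The same data could then support two different messages, and the choice could be made after the result is known.

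**Working it through.** **Inputs.** From Statistical Analysis: n = 15, one-tailed 5%, SD 10%, mean temperature change 0.7°C. From Hypothesis: threshold 10% per °C. The documents do not say whether the 10% SD refers to variation between children or to change within a child. I therefore assume a per-degree SD between 10% (a full 1°C change) and 10/0.7 = 14.3% (a constant 0.7°C change).

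**Step 1: the plan's own figure.** For a paired t-test with standardised effect 10/10 = 1, the exact calculation gives n = 8 one-sided (power 0.815) and n = 10 two-sided (power 0.803). The stated 10 is close to the first and equal to the second. Then 10/0.7 = 14.3, rounded up to 15, as stated. A direct one-sided calculation for a 7% change also gives 15 (power 0.824). All of these test a 10% effect against zero, not against the 10% threshold.

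**Step 2: precision.** SE = SD/√15 and t(14; 0.95) = 1.761.
- SD 10%: SE = 2.58; 90% half-width = 1.761 × 2.58 = 4.5 points.
- SD 14.3%: SE = 3.69; 90% half-width = 1.761 × 3.69 = 6.5 points.

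An estimate of 7% per °C thus has a 90% interval of 2.5 to 11.5 or 0.5 to 13.5. In both cases it is above zero and not shown to exceed 10%.

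**Step 3: chance of a result above zero but not shown to exceed 10%.** With true cost m, this is P(T′ > 1.761 with noncentrality m/SE) minus P(T′ > 1.761 with noncentrality (m − 10)/SE), on 14 degrees of freedom.

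| True cost per °C | SD 10% | SD 14.3% |
|---|---|---|
| 5% | 58% | 36% |
| 7% | 82% | 56% |
| 10% | 93% | 77% |

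**Step 4: what a non-significant result means depends on the reference value.**
- Test against 10%: a true 15% per °C is missed in 42% (SD 10%) to 64% (SD 14.3%) of studies. Estimates up to 10 + 4.5 = 14.5% or 10 + 6.5 = 16.5% would not reject the null.
- Test against zero: a true 10% is missed in 2% to 18%. If the observed SD equals the assumed one, the largest non-significant estimate is 4.55% or 6.50%. The one-sided 95% upper limit is then at most 2 × 4.55 = 9.1% or 2 × 6.50 = 13.0%. Non-significance rules out 10% in the first case but not in the second.

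**Step 5: an interval rule.** A conclusion of below 10% needs an estimate under 10 − 4.5 = 5.5% or 10 − 6.5 = 3.5%.

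| True cost per °C | Concludes below 10% (SD 10% / 14.3%) | Inconclusive (SD 10% / 14.3%) |
|---|---|---|
| 0% | 98% / 82% | not tabulated |
| 5% | 58% / 36% | 42% / 64% |
| 10% | 5% / 5% | 90% / 90% |
| 15% | not tabulated | 42% / 64% |

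An 80% chance of concluding below 10% needs 8 to 15 children if the true cost is zero, and 27 to 52 if it is 5% per °C.

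**The case against.** The sentences at issue are statements of significance, outside the Statistical Analysis section and cautiously worded. A reader might infer that the plan treats non-significance as proof of a low cost, but no sentence says so. What stands is that nothing says how the null would be shown to be true.

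A reader might also infer that the Introduction tests against zero. It never mentions zero, and its word for a notable increase could mean the 10% threshold. Its second branch speaks only of an increase, so the wording remains unreconciled, but two separate decision rules are not established. Nor are the two messages opposites: a trial of treating against not treating fever also puts treatment in question. They differ in strength and in the next step.

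The largest figure, 64% missed at a true 15% per °C, requires a test against 10%. The plan describes a comparison with and without fever. Tested against zero, the miss rate at 15% is about 1% at most over the assumed SD range, so 64% should not be quoted as a property of the planned test.

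Recruitment beyond 15 is intended, and estimating the per-degree change is the primary outcome. With 30 children and SD 14.3%, a result non-significant against zero would have an upper limit of at most 2 × 1.699 × 14.3/√30 = 8.9%. More children ease the problem, but they supply neither a rule nor a common trigger.

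**Conclusion.** The concern holds as a gap in the conclusion rule and as a difference in wording between sections. It does not show that the plan equates non-significance with proof. The missing criterion and the differing triggers are on the page and rest on no assumption. The probabilities rest on n = 15, one-tailed 5%, a common temperature change, and an assumed per-degree SD of 10% to 14.3%.

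On those assumptions, the result that can be read two ways is likely at true costs of 5% to 10% per °C, where the study's interest lies; the Background cites 10% in adults. Whether a non-significant result excludes a 10% cost depends on the SD and on a reference value the plan leaves open. This is a should-fix: no allocation or stopping decision hangs on these sentences, but the study's practical message does.

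**What to change.** Use one trigger, the 10% per °C threshold, in the Introduction, Background, Hypothesis, and Outcomes and Significance sections. In Statistical Analysis, name the primary analysis (the paired comparison or the regression) and report from it the mean percentage change per °C with a two-sided 90% confidence interval, which matches the one-tailed 5%. Then state one rule:

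- below 10% per °C only if the upper limit is below 10%;
- above 10% per °C only if the lower limit is above 10%;
- otherwise inconclusive, with no inference about treatment.

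This needs no new data or patients, only wording in those sections. The cost is candour about how often the study will not settle the question, and the plan should state the inconclusive rates from Step 5 with their SD range. If the investigators want a good chance of concluding below 10% when the true cost is about 5% per °C, the 15-child minimum is too small over the assumed SD range, and the open-ended recruitment aim should be set with that in mind.
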